Number of Prescribing Centres:	Prescribers that meet agreed site participation standards will be selected from the 232 Genitourinary Medicine (GUM) clinics in England. The decision to include a prescriber will be made by the sponsor. The aim is to establish a wide geographical spread of trial sites with prescribers in urban and rural settings; in high, medium and low throughput clinics; and in clinics with predominantly MSM and non-MSM eligible populations.
Duration of the trial:	4.5 years (33 month recruitment period)
Dose and Route of Administration:	
Drug: Tenofovir Disoproxil (TD)/ Emtricitabine (FTC). Each film-coated tablet contains 200 mg of emtricitabine and 245 mg of tenofovir disoproxil (as maleate).
 
Regimen: Daily or event-based regimens (EBD). Daily involves taking 245 mg TD and 200mg FTC once a day. EBD will involve taking a double dose before sex and then single doses 24 and 48 hours after the initial dose. EBD is not recommended for heterosexual men, heterosexual women, and transgender men due to lack of trial efficacy data to support this regimen in these risk groups.
 
Route of administration: Oral

Trial Outcomes:	
 1. Proportion of GUM clinic attendees that meet PrEP eligibility criteria, the proportion that is prescribed PrEP per year and the duration of PrEP-eligibility and PrEP-use among users. 2. HIV and STIs: 
 a. HIV diagnoses reported by sites and identified through the national surveillance dataset b. STI diagnoses (gonorrhoea, chlamydia, syphilis and hepatitis C) reported in the national surveillance dataset 3. Adverse Events 
 a. Serious suspected adverse drug reactions reported using the yellow card system b. Antiretroviral resistance associated mutations in participants with incident HIV infection

GENERAL TRIAL INFORMATION**Chief Investigator:**

[name]
Chelsea & Westminster NHS Foundation Trust
[name],
[name]

Sponsor:

Chelsea & Westminster NHS Foundation Trust
[name],
[name]

Funder:

NHS England

Trial management:

Chelsea & Westminster NHS Foundation Trust
[name],
[name]

Email: [contact]

Medical Expertise:

[name] - Public Health England
Email: [contact]

[name] - University of Manchester
Email: [contact]

[figure not shown]
[name] - Public Health England
Email: [contact]

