3.1 Sites

In order to include all sites from across urban and rural settings and in high, medium and low throughput clinics, all GUM clinics in England (Level-3 Sexual Health Services) will be eligible to take part in the trial, providing they meet the following criteria:

1. Access to 4th generation HIV ELISA tests,
2. Access to a local laboratory that can analyse serum creatinine,
3. PrEP SHHAPT O codes implemented into existing patient record systems before participants are recruited,
4. Reporting PrEP codes with clinic activity and diagnoses using enhanced GUMCAD to PHE on a monthly basis,
5. Have suitable systems in place to prescribe and dispense PrEP to participants,
6. Ensure adequate capacity to deliver STI and HIV testing according to standard of care, in line with established clinical practice,
7. Comply with good clinical practice requirements.

Sites will be required to:

- Screen clinic attendees for PrEP-eligibility at each new episode of care
- Conduct patient recruitment and consent procedures,
- Assign O codes as specified in the GUMCAD technical specification,
- Complete the relevant data entry into the trial database (eCRF),
- Report recruitment figures monthly to the trial sponsor,
- Report any suspected or confirmed HIV seroconversion in a trial participant to the trial sponsor within a week of the suspected or confirmed positive HIV test result. Site should also ensure the patient is added to the HIV & AIDS Reporting System (HARS) as per routine clinical practice,
- Provide the sponsor with at least monthly PrEP-dispensing reports.

Participants will only be able to access PrEP through approved participating GUM clinics. The Sponsor and Public Health England will have overall responsibility for site and investigator selection, but the decision to include a site will be taken by the Sponsor.

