8.3 Statistical Analysis

All analyses will be performed using STATA data analysis and statistical software version 13 or higher. Preliminary data review, analysis and presentation may be conducted throughout study duration at the request of the Trial Steering Committee. A detailed description of the analyses to be performed is outlined in the Statistical Analysis Plan (SAP). The analysis will address all outcomes of the trial and a descriptive baseline analysis will also be performed. Safety data will be extracted from 'yellow card' submissions.

To address the trial objectives, the following analyses will be undertaken:

- 1) PrEP eligibility: the total eligible population (numerator) will be estimated from the 'total' GUM attending clinic population (denominator). The clinic attending population will be categorised as 'eligible' or 'non-eligible' in participating clinics. Therefore, to estimate numbers eligible for PrEP among the 'total' GUM clinic attending population, a finite population correction will be used based on the total number of GUM clinics with post-hoc stratification weighting as necessary to account for observed differences between the sample and population with respect to important patient characteristics such as sexual orientation and age group.
- 2) Uptake of PrEP: The numerator is the population taking up an offer of PrEP, and denominator is the eligible population in participating GUM clinics. The uptake of PrEP will be estimated using a binomial generalised linear model with logarithmic link function, taking into account heterogeneity of clinics. An analysis of the predictors of PrEP uptake will be made, and will include time as a variable. There is a dynamic aspect to PrEP uptake (e.g. starting, stopping, restarting) which will be taken into consideration.
- 3) Duration of PrEP eligibility and use: Participants in the trial can be in one of three states: 'eligible for PrEP and on PrEP', 'eligible for PrEP but not on PrEP', and 'currently ineligible for PrEP'. Participants will move between these states. The analysis will use a multi-state model to estimate the

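### The national eligible count leaves clinic-selection error out of its interval, and the plan gives no class or rule for attendees who were never assessed for eligibility

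*Combined protocol and SAP*

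**What the plan says.** **Estimation.** Section 8.3, item 1, estimates the number eligible among attendees of all GUM clinics from those in participating clinics. The method is "a finite population correction will be used based on the total number of GUM clinics with post-hoc stratification weighting as necessary". The weighting is to deal with differences between sample and population in "important patient characteristics such as sexual orientation and age group". No clinic-level weighting variable is named.

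**How clinics enter.** The Synopsis (Number of Prescribing Centres) states: "Prescribers that meet agreed site participation standards will be selected from the 232 Genitourinary Medicine (GUM) clinics in England". It adds: "The decision to include a prescriber will be made by the sponsor". The intention is purposive spread: "The aim is to establish a wide geographical spread of trial sites with prescribers in urban and rural settings". Section 3.1 opens the trial widely ("all GUM clinics in England (Level-3 Sexual Health Services) will be eligible to take part in the trial, providing they meet the following criteria") and then lists seven conditions, among them PrEP coding, monthly enhanced GUMCAD reporting, dispensing systems and testing capacity. No random draw or selection probability is described.

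**Classification.** Section 8.3 has two classes: "The clinic attending population will be categorised as 'eligible' or 'non-eligible' in participating clinics". Section 3.1 requires sites to "Screen clinic attendees for PrEP-eligibility at each new episode of care". Neither section gives an expected completeness or says how an attendee without an eligibility code is treated.

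**Planned precision.** Section 8.1 gives ±480 to ±1150 for the total eligible population, from simulations, and ±3% for uptake.

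**The concern.** A finite population correction reduces the standard error because part of the population has been observed. It gives an honest interval if the clinics not observed resemble those observed, once weighted. Here the clinics that join are the ones able to code, report, dispense and test, and the sponsor chooses among them. Those features could well go with throughput, region and the share of MSM among attendees, and hence with the eligible rate. Weighting on patient orientation and age may not remove that link, and the interval has no term for what is left.

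The two-class scheme raises a second problem. Eligibility is read from routine GUMCAD codes. People who take PrEP also have an eCRF record of enrolment and dispensing (Sections 5.3, 8.5 and 8.6), while people who decline rest on the routine code alone. Less complete coding of decliners is therefore plausible, though the documents do not report it.

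The proportion eligible belongs to the first-listed outcome (Section 8.2), and Section 6.2 sends the trial's data to commissioners. Uptake uses the eligible population in participating clinics as its denominator, so under-coding would affect it as well.

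**Working it through.** **Inputs from the documents.** 232 GUM clinics (Synopsis). About 10,000 eligible MSM across all clinics, with non-MSM eligible at 20% of that (Section 8.1), so 10,000 × 1.2 = 12,000 in total. Planned half-width ±480 to ±1150.

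**Assumed, because the documents do not give them.** m, the number of joining clinics; d, the difference between joining and non-joining clinics that remains after weighting, in between-clinic SDs; a, the share of eligible attendees coded eligible; r, the eligible rate in non-joining clinics divided by that in joining clinics.

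**1. The plan's own figure.** A Poisson half-width for a count T is 1.96 × √T. For T = 500 this is ±43.8, which matches the lower sub-group figure of ±44; ±64 needs a design effect of (64/1.96)²/500 = 2.13. For T = 12,000 it is ±215, so ±480 and ±1150 imply design effects of 5.0 and 28.7 (6.0 and 34.4 if T = 10,000). The simulation's clinic numbers, between-clinic variance and use of the correction are not stated. The national figure can therefore be neither reproduced nor called wrong.

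**2. Coverage under selection.** Let f = m/232. In between-clinic SD units, with equally weighted clinics and normal theory:

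- bias of the all-clinic estimate = (1 − f)d
- standard error with the correction = √((1 − f)/m)
- bias/SE = d√(m(1 − f))
- coverage = Φ(1.96 − bias/SE) − Φ(−1.96 − bias/SE)

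Example, m = 116 and d = 0.25: bias = 0.5 × 0.25 = 0.125; SE = √(0.5/116) = 0.0657; ratio = 1.90; coverage = Φ(0.06) − Φ(−3.86) = 52%. Without the correction, 1.96 is replaced by 1.96/√(1 − f), and coverage is 81%.

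| m | Correction factor √(1 − f) | With correction: d = 0 | d = 0.10 | d = 0.25 | d = 0.50 | Without: d = 0.25 | d = 0.50 |
|---|---|---|---|---|---|---|---|
| 116 | 0.71 | 95% | 88% | 52% | 3% | 81% | 15% |
| 174 | 0.50 | 95% | 90% | 62% | 9% | 99% | 73% |
| 209 | 0.31 | 95% | 93% | 79% | 38% | >99% | >99% |

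**3. Uncoded attendees.** If uncoded is read as non-eligible, the shortfall is 12,000 × (1 − a): 600 at a = 0.95, 1,200 at 0.90 and 2,400 at 0.80. The first exceeds the lower end of the planned half-width and the other two exceed the upper end.

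**4. Uptake in participating clinics.** Let u be true uptake and c the share of decliners coded, with all takers coded. Then a = u + (1 − u)c and observed uptake = u/a. With u = 50%, c = 0.9, 0.8 and 0.6 give a = 0.95, 0.90 and 0.80, and observed uptake of 52.6%, 55.6% and 62.5%. The last two lie outside the planned ±3%.

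**5. Net direction of the national count.** Estimate/truth = a/(f + (1 − f)r). With f = 0.5 and r = 0.5 (joining clinics have the higher eligible rate) it is 1.33, 1.20, 1.07 and 0.80 for a = 1, 0.9, 0.8 and 0.6. With r = 1 it equals a. Either sign is possible.

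**The case against.** - **The correction suits the stated target.** The target is a total over a finite set of 232 clinics. If joining is ignorable after weighting, the interval covers 95%, and an interval without the correction over-covers when most clinics join. This stands. A reader might take the correction factors of 0.71 to 0.31 as showing intervals 29% to 69% too narrow. Those figures are only the size of the correction and measure error only if the uncorrected interval is the right one.
- **Selection bias shrinks as clinics join.** This also stands: the bias is (1 − f)d, and Section 1 wants as many clinics as possible. At d = 0.25 coverage improves from 52% to 79% between 116 and 209 clinics. It is still well short of 95%.
- **Dropping the correction is no cure.** At 116 clinics coverage is 81% for d = 0.25 and 15% for d = 0.50. The main remedy has to be clinic-level weighting.
- **The plan requires screening and does not say that uncoded means non-eligible.** Correct. A reader might infer that unassessed attendees are forced into the non-eligible class. The text is silent on them, and Sections 8.5 and 8.6 treat eligibility, offer and prescribing as separate GUMCAD items. The fault is a missing rule.
- **The plan recognises the bias.** Section 8.3 describes differences in risk mix between clinics and refers their handling to the SAP. No separate SAP text is in the document available here, so one cannot say that it lacks clinic-level adjustment. The weighting list is also open-ended. Even so, the method that Section 8.3 does set out names patient characteristics only, although Section 8.1 counts clinic and geographical area among the covariates of major interest.

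**Conclusion.** The point holds in a conditional form. As described, the interval for the national eligible count has no allowance for clinic selection. It under-covers if joining remains related to the eligible rate after weighting: to about 52% at 116 clinics and 79% at 209 for a difference of 0.25 SD, and not at all if joining is ignorable. The values of m and d are illustrative.

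The absence of a not-assessed class matters on its own. Modest under-coding, if read as non-eligible, could move the count by as much as or more than the planned precision, and it would overstate uptake if decliners are coded less completely than takers. The coding shares are assumed.

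Two stronger conclusions are not supported. One is that the national count is biased low: under-coding pushes it down, but over-representation of high-eligibility clinics pushes it up, so the net sign is unknown. The other is that the correction or the national weighting distorts uptake: uptake is defined within participating clinics, so only the coding problem reaches it.

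This is a cheap improvement to the first-listed outcome. It does not show that the planned analysis is invalid.

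**What to change.** 1. Weight to all GUM clinics on clinic-level variables (region, throughput, MSM share of attendees, bacterial STI rate) as well as patient characteristics. GUMCAD reporting is mandatory (Section 8.5), so these should be available for non-joining clinics.
2. Report the interval with and without the finite population correction, and add a sensitivity range in which the eligible rate in non-joining clinics differs from that in joining clinics by stated amounts.
3. Classify attendees as eligible, assessed and not eligible, or not assessed. Report the share assessed by clinic.
4. Give bounds for the eligible count and for uptake under stated assumptions about those not assessed, including all and none of them eligible.
5. Keep any imputation from STI markers as a sensitivity analysis. Section 1 calls that proxy considerably uncertain (33% from STI diagnoses against as much as 60% from clinic surveys).

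The cost is SAP wording, analyst time and a wider reported range. No new data collection should be needed.

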Methodology:	
Potentially eligible participants will be identified following a clinical risk assessment primarily during routine sexual health clinic visits, but may be contacted following review of the clinic database. Other methods such as outreach activities, and through community organisations and social media, may be used to identify potentially eligible patients for referral to a local genitourinary medicine (GUM) clinic.
 
Participants who consent to enrol in the trial will be allocated a trial ID and be prescribed PrEP at a GUM clinic. Routine clinic records and the standard data routinely extracted into the national GUM Clinic Activity Dataset (GUMCAD) database will be used to capture clinical and prescribing data. The subject ID will be linked to relevant GUMCAD record using the subject ID number, SOUNDINDEX code and semi-anonymised GUM clinic number in the trial database. Adverse events will be reported using the 'Yellow card' system and logged in the trial database for central monitoring. Dispensing data will also be collected for central monitoring.
 
In line with national guidance and the evidence from efficacy trials, at each visit participants will be offered PrEP as part of an active risk reduction intervention, including health education and safer sex promotion, to reduce and modify high risk behaviour. This may include the provision of free condoms, behaviour change interventions, other biomedical interventions such as post-exposure prophylaxis where relevant, the diagnosis and treatment of sexually transmitted infections (STIs), and regular HIV testing.
 
Participants who are starting PrEP are recommended to have a one month safety check (which can be done in person, on the phone or via email) and then

	quarterly visits depending on ongoing risk, with clinical risk assessments and tests performed according to the visit schedule and recommended clinical practice.
Planned Sample Size:	13,000 participants

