5 ASSESSMENTS AND FOLLOW-UP PROCEDURES

5.1 Patient Identification

Potentially eligible individuals will be identified by local investigators during routine enquiry about HIV risk at sexual health clinic visits. Potentially eligible individuals may also be identified through outreach activities, by community organisations and through social media. Individuals are also likely to self-identify their need for PrEP as mainstream media has, and will continue to report the plan to implement PrEP through a large scale trial. The participant information sheet will be publicly available through the trial website and individuals will be able to read this prior to visiting clinic, or whilst waiting to be seen. The website will also provide details of participating clinics.

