5.4 Assessments and Procedures

All assessments required to support PrEP are established practice in GUM clinics based on clinical evidence, including discussion of the trial regimen (daily or EBD). These are summarised in the Table of Standard Assessments and Trial Procedures.

Trial procedures are those that support collection of informed consent, review of inclusion/exclusion criteria which includes checking the record of previous HIV test results in the clinic, completion of the trial register/entry onto trial database and accounting for drug dispensed through the trial. It is envisaged that the large majority of individuals will enrol at a clinic they have previously visited but in circumstances where this is not the case a self-report of a preceding HIV test at another clinic will be accepted and should be checked. In exceptional circumstances heterosexual populations at imminent risk of acquiring HIV may present to clinic

with no previous HIV test and start PrEP on the basis of a negative point of care test, whilst awaiting the result of the 4th generation HIV ELISA following a clinical risk assessment.

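### Projecting the eligible share from participating clinics to all GUM clinics biases the national total upward to the extent that coverage is incomplete and the trial draws eligible people in from other clinics

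*Combined protocol and SAP*

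**What the plan says.** Section 8.3 item 1 estimates the number of people eligible for PrEP in the whole GUM attending population. The observation base is narrower: "The clinic attending population will be categorised as 'eligible' or 'non-eligible' in participating clinics". To reach the whole population, "a finite population correction will be used based on the total number of GUM clinics", with post-stratification weighting where needed on "important patient characteristics such as sexual orientation and age group".

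Other sections describe who will come to those clinics:

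- Section 3.1: "Participants will only be able to access PrEP through approved participating GUM clinics".
- Section 5.1: "The website will also provide details of participating clinics". It also expects people to recognise their own need for PrEP.
- Synopsis, Methodology: outreach, community organisations and social media "may be used to identify potentially eligible patients for referral to a local genitourinary medicine (GUM) clinic".
- Section 5.4: for people enrolling at a clinic that is new to them, "a self-report of a preceding HIV test at another clinic will be accepted and should be checked". The same sentence expects most people to enrol where they are already known.
- Section 5.9 acknowledges that patients change services, expects some of this during the trial, and notes that GUMCAD numbers are specific to a clinic.

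Section 8.3 also warns of two biases. Risk spectrum bias is a differing risk mix between clinics or over time. Health-seeking behaviour bias is a difference between those who come to services and those who do not. Their handling is left to a statistical analysis plan that is not included in the document reviewed.

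**The concern.** The projection treats participating clinics, after weighting, as standing in for the rest. The trial gives eligible people a reason to leave a non-participating clinic for a participating one. Those who do so raise the eligible share where it is measured, and that share is then applied to clinics that have lost them.

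The two adjustments named do not address this. A finite population correction changes the standard error and leaves the point estimate alone. Weighting by orientation and age leaves the bias within each stratum, because movers are selected on eligibility within the stratum: an eligible man who moves raises the eligible share among MSM of his age group.

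Eligibility is the first objective and the first outcome, and the stated aim is to test consensus estimates of PrEP need so that commissioning can be decided. The bias does not shrink as more participants are recruited. Newcomers who came in order to obtain PrEP could also raise the uptake proportion in item 2.

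**Working it through.** **The plan's own figure.** Section 8.1 gives a precision of ±480 to ±1150 for the total eligible population. It comes from simulations whose clinic-level inputs are not reported, so it cannot be reproduced. A simple Poisson half-width is 1.96 × √10,000 = 196, or 1.96 × √12,000 = 215. The stated range therefore implies a variance inflation of about 6 to 34 on 10,000, or 5 to 29 on 12,000. The lower sub-group figure of ±44 does match 1.96 × √500 = 43.8.

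**Inputs**

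- T, true eligible total: 12,000. Section 8.1 gives about 10,000 MSM plus non-MSM at 20% of that, so 10,000 + 2,000.
- p, eligible share of attendees: 0.33 for illustration, inside the 20% to 60% range that Section 8.1 uses for MSM.
- w, share of GUM attendees served by participating clinics: not given, assumed. The Synopsis counts 232 GUM clinics but does not say how many take part.
- m, share of eligible people at non-participating clinics who move to a participating one: not given, assumed.

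**Derivation.** Suppose the eligible share is the same everywhere before the trial. Participating clinics then serve wT eligible people and other clinics serve (1−w)T. After movement, participating clinics see T[w + m(1−w)] eligible people.

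- *Count expansion* (divide the count by w): estimate/truth = [w + m(1−w)]/w.
- *Proportion applied to a fixed attendee total* (movers also enter the denominator): estimate/truth = [w + m(1−w)]/[w + m(1−w)p].

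Both ratios equal 1 when m = 0 or w = 1 and exceed 1 otherwise. Outcome 1 is worded as a proportion, so the second form is the closer reading. The two forms converge where p is small, as it may be among non-MSM attendees.

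**Numbers at m = 10%**

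| w | Proportion, p = 0.33 | Bias | Count expansion | Bias |
|---|---|---|---|---|
| 0.9 | 0.91/0.9033 | +89 | 0.91/0.9 | +133 |
| 0.7 | 0.73/0.7099 | +340 | 0.73/0.7 | +514 |
| 0.5 | 0.55/0.5165 | +778 | 0.55/0.5 | +1,200 |

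Moving p from 0.2 to 0.6 changes the proportion form from +106 to +53 at w = 0.9, from +408 to +201 at w = 0.7, and from +941 to +453 at w = 0.5.

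**Movement needed for the bias to equal the stated precision** (proportion form / count expansion)

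| w | reaches 480 | reaches 1150 |
|---|---|---|
| 0.5 | 6.1% / 4.0% | 15% / 9.6% |
| 0.7 | 14% / 9.3% | 35% / 22% |
| 0.8 | 24% / 16% | 60% / 38% |
| 0.9 | 55% / 36% | not reachable / 86% |

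**The case against.** The strongest reply is that the bias may be negligible. Every Level-3 GUM clinic may join (Section 3.1), the background section asks for the widest possible participation, and Section 5.4 expects newcomers to be a minority. With full coverage the bias is zero, and at 90% coverage it would take 36% to 55% movement to reach even ±480. This stands, and it is why the point must be conditional.

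It can also be said that Section 8.3 already covers the matter. Risk spectrum bias includes a change in a clinic's mix over time, and an influx of eligible people is such a change. That overlaps, but neither definition mentions the trial moving people out of the very clinics to which the result is projected. The list of weighting variables is also open-ended. Because the separate analysis plan could not be read, it cannot be said that no handling exists, only that none is described here. The transfer procedure in Section 5.9 guards against double enrolment and does nothing to the eligibility count.

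Some tempting readings go too far:

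- A reader might infer that the national total is too high as a matter of fact. The documents give neither w nor m, and other errors, such as incomplete coding of eligible attendees, could pull the other way.
- A reader might infer that everyone referred from outreach is counted twice. The Synopsis speaks of referral to a local clinic, and such people need not have left another GUM clinic.
- A reader might infer that the eligible count is the main budget input. Section 8.4 lists HIV risk of those taking PrEP, effectiveness, risk compensation and duration of use, and does not list the count.

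**Conclusion.** The point holds in conditional form. To the extent that coverage is incomplete and eligible people move in from non-participating clinics, item 1 overstates the national eligible total, and the named adjustments do not correct this. With 10% movement the proportion form gives from about +89 (90% coverage) to +778 (50% coverage) on 12,000; count expansion gives +133 to +1,200. Set against ±480 to ±1150, that runs from unimportant to as large as the stated precision.

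The sizes rest on assumed w and m, on p = 0.33, and on equal eligible shares at all clinics before the trial. The upward direction of this one component follows from the algebra under that last assumption; the net sign of all errors in the total does not.

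**What to change.** In Section 8.3 item 1, add a sensitivity estimate from GUMCAD, which already covers all GUM clinics:

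1. Take attendees with a record at that clinic before it opened to the trial. For non-participating clinics use a matched date.
2. Estimate the eligible share in this group at participating clinics.
3. Project it only to the same prior-record group across all GUM clinics. It should not be applied to all attendees: population A requires a negative HIV test at an earlier episode of care in the preceding year (Section 3.3), so people with a prior record are more likely to qualify, and a wider projection could raise the estimate.
4. Report it beside the all-attendee projection, with clinic coverage and with pre-trial against in-trial attendance by participation status.
5. In item 2, report uptake by prior-record status, which is available for all eligible attendees including those who decline.

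A new question at enrolment is not advised. It would miss decliners, who belong in the uptake denominator, and the more than 7,000 people enrolled in the first 8 months (Section 8.1).

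The cost is one further run of the estimator and some descriptive tables, with no new data collection. The restricted estimate leaves out genuinely new attendees, so it must not be presented as a lower bound on the whole total.
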